7.1 Primary endpoint(s)

7.1.1 Definition

The adverse event will be coded using MedDRA dictionary.

Absolute and percent change from baseline will be calculated for both the vital signs and laboratory parameters.

7.1.2 Analysis

The adverse events will be analyzed using frequencies and percent divided by SOC, and PT code using the TESS approach.

The vital signs will be presented using summary statistics by visit.

Safety laboratory parameters will be presented using shift tables.

7.1.3 Presentation

The adverse events will be present using frequency tables.

7.2 Secondary Endpoints – CTSI and mCTSI

7.2.1 Definition

Balthazar score is classified according to the table below

Grade	CT Finding Balthazar	Points
A	Normal Pancreas	0
B	Enlargement of Pancreas	1
C	Inflammatory changes in pancreas and peripancreatic fat	2

D	Ill-defined single peripancreatic fluid collection	3
E	Two or more poorly defined peripancreatic fluid collections	4

Pancreatic Parenchymal Necrosis is classified as:

Pancreatic Necrosis	Points
None	0
<30%	2
30-50%	4
>50%	6

The CTSI score is the sum of the Balthazar and Pancreatic Necrosis scores:

- 0-3: mild acute pancreatitis
- 4-6: moderate acute pancreatitis
- 7-10: severe acute pancreatitis

Change for the category of the severity of acute pancreatitis by CTSI score will be calculated from baseline to day 5 and later dates as necessary.

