### 5.2 Discharge Criteria

The patient randomized to receive CM4620-IE should remain in the hospital until all 4 doses of CM4620-IE have been administered, and a CECT of the pancreas has been performed. The suggested criteria for discharging patients from the hospital are:

- Abdominal pain has resolved
- Normal oral diet is tolerated
- There is no clinical or laboratory evidence of an infection

If the patient is ready to be discharged before all 4 doses of CM4620-IE have been administered or the CECT of the pancreas has been performed, the PI or treating physician should contact the Medical Monitor prior to discharging the patient.

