**All patients will undergo a CECT of the pancreas on Day 5.**

- The CECT will be performed on Days 6 or 7 if unable to be performed on Day 5
- If the PI wishes to discharge a patient randomized to supportive care only before Day 5, a CECT should be performed prior to discharge
- If the PI wishes to delay the CECT beyond Day 7, the Medical Monitor should be contacted

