### **8.11.14 Contrast-Enhanced Computed Tomography (CECT) of the Pancreas**

All patients will undergo a CECT of the pancreas at Screening, and on Day 5. The Screening CECT may have been performed more than 18 hours prior to consent and not repeated after consent for patients-specific safety considerations. The Day 5 CECT will be performed on Days 6 or 7 if unable to be performed on Day 5. The CECT will be performed prior to discharge if discharge is planned sooner than Day 5.

The recommended CECT protocol:

- A non-ionic contrast bolus of 100-150cc will be administered at 3-5cc/second
- Slice thicknesses will be 5 mm or less and will be obtained through the pancreas during the pancreatic phase (35 seconds after the start of the non-ionic contrast bolus) and through the entire abdomen during the portal venous phase (50 to 70 seconds after the start of the non-ionic contrast bolus) to visualize the pancreas and surrounding tissue

The CECT protocol may be altered to local standard of care. If the patient has acute kidney injury or renal failure, the CECT may be done at the discretion of the local radiologist, treating physician or PI without the non-ionic contrast bolus or with a lower amount of non-ionic contrast. The PI or treating physician may also elect to change the timing of the Day 5 CECT due to patient-specific safety considerations to later than Day 7, but must inform the Medical Monitor of the decision. The PI or treating physician may also elect not to perform the CECT because of futility considerations, e.g., the patient is unlikely to survive in the next 48 hours, but must discuss the decision with the Medical Monitor.

Patients with a history of acute pancreatitis who have SIRS or a SpO2 <96% with a FiO2 of 21% (room air) to 27% or SpO2 <97% with a FiO2 ≥28% at Screening must have no evidence of pancreatic necrosis by CECT performed in the 18 hours prior to consent or after consent and before Day 1. The Screening CECT may have been performed more than 18 hours prior to consent and not repeated after consent for patients-specific safety considerations.

The Day 5 CECT and the CECT performed at screening will read by a blinded central reader; they will also be read locally and may be used by the PI or treating physician, as needed, for patient management.

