### C. Imaging

6. The indication for initial CT assessment in acute pancreatitis can be: 1) diagnostic uncertainty, 2) confirmation of severity based on clinical predictors of severe acute pancreatitis, or 3) failure to respond to conservative treatment or in the setting of clinical deterioration. Optimal timing for initial CT assessment is at least 72-96 hours after onset of symptoms. (GRADE 1C, strong agreement)
7. Follow up CT or MR in acute pancreatitis is indicated when there is a lack of clinical improvement, clinical deterioration, or especially when invasive intervention is considered. (GRADE 1C, strong agreement)
8. It is recommended to perform multi-detector CT with thin collimation and slice thickness (i.e. 5mm or less), 100-150 ml of non-ionic intra-venous contrast material at a rate of 3mL/s, during the pancreatic and/or portal venous phase (i.e. 50-70 seconds delay). During follow up only a portal venous phase (monophasic) is generally sufficient. For MR, the recommendation

is to perform axial FS-T2 and FS-T1 scanning before and after intravenous gadolinium contrast administration. (GRADE 1C, strong agreement)

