4.2 Sample Size Justification

This open-label study will enroll 24 patients. The sample size was selected based on practical considerations to initially evaluate the safety, efficacy and pharmacokinetic profile of CM4620-IE in patients with acute pancreatitis and accompanying SIRS. This study is not powered for analysis of study data with inferential statistics

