4.8 Handling of Drop-outs, Missing Data and Outliers

Outliers will be included in summary tables and listings, and will not be handled separately in any analyses. No imputation of missing data will be performed (however, will data entered in unscheduled visit be placed to the nearest applicable visit with missing values).

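### The follow-up CTSI comparison can be biased, because the SAP has no rule for scans taken before Day 5 or for patients too ill to be scanned

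*SAP*

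**What the plan says.** SAP 7.2.1 defines the endpoint: "Change for the category of the severity of acute pancreatitis by CTSI score will be calculated from baseline to day 5 and later dates". The sentence goes on to allow later dates as needed. It sets no analysis window. It has no rule for a scan before Day 5 and no category for a patient without a follow-up scan. SAP 7.2.2 specifies no test.

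The protocol makes the timing and existence of that scan depend on the patient's course:

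- Protocol 5.2, drug arm: "The patient randomized to receive CM4620-IE should remain in the hospital until all 4 doses of CM4620-IE have been administered", and until the scan is done. The same section foresees discharge before either is complete, after contact with the Medical Monitor.
- Protocol 8.6, control arm: "If the PI wishes to discharge a patient randomized to supportive care only before Day 5, a CECT should be performed prior to discharge".
- Protocol 8.11.14 repeats the pre-discharge scan without naming an arm. It also lets the scan move beyond Day 7 for safety reasons, with no upper limit.
- Protocol 8.11.14, both arms: "The PI or treating physician may also elect not to perform the CECT because of futility considerations". The example given is a patient not expected to live another 48 hours.

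On missing data, SAP 4.8 says: "No imputation of missing data will be performed". It adds that data from an unscheduled visit go to the closest applicable visit that lacks a value.

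**The concern.** Two features of the follow-up scan are settled after randomization: when it is done and whether it is done.

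Timing matters because Inclusion Criterion 3 requires no pancreatic necrosis at screening. Baseline necrosis points should therefore be 0, and the change in CTSI category depends on what is newly visible at follow-up. A scan taken earlier has had less time to show it. The expected stay differs by arm, so early scans are more likely among controls. Under SAP 4.8 such a scan can appear in the Day 5 column with nothing to mark it.

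Omission matters because the patients left out for futility are the worst cases. With no imputation and no row for them, an arm that loses such a patient shows a milder CTSI distribution than it really had. Protocol 1.6 says the design will support a dose-response analysis of efficacy as well as safety, so readers will compare these columns.

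**Working it through.** **Planned numbers.** SAP 4.2: "This open-label study will enroll 24 patients". Cohort sizes (SAP 3.2): 4 + 4 + 8 + 8 = 24, which reproduces the stated total. Splitting each cohort 3:1 gives 3 + 3 + 6 + 6 = 18 drug patients (6 low dose, 12 high dose) and 1 + 1 + 2 + 2 = 6 controls. The plan states no effect size, event rate or power ("The sample size was selected based on practical considerations"), so there is no power figure to check.

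**Weight of one patient.** Controls 1/6 = 16.7 points; low dose 1/6 = 16.7; high dose 1/12 = 8.3; all drug patients 1/18 = 5.6.

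**Scan clock.** The fourth dose starts 72 h (±1 h) after the first and runs for 4 h. A scan after four doses is therefore at least 71 + 4 = 75 h after the first dose (76 h nominal), and later than that from pain onset. A control's pre-discharge scan has no stated minimum. It may still lie more than 72 h from pain onset, because onset precedes randomization.

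**Illustration with no true effect (all rates assumed).** Suppose 6/18 drug patients and 2/6 controls are truly moderate or severe, so the true difference is 0. A positive difference makes the drug look worse.

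| Event | Drug | Control | Drug minus control |
|---|---|---|---|
| One early-scanned control read as mild | 6/18 = 33.3% | 1/6 = 16.7% | +16.7 points |
| One severe control not scanned | 6/18 = 33.3% | 1/5 = 20.0% | +13.3 points |
| One severe drug patient not scanned | 5/17 = 29.4% | 2/6 = 33.3% | −3.9 points |
| One severe patient not scanned in each arm | 5/17 = 29.4% | 1/5 = 20.0% | +9.4 points |

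The sign depends on which arm is affected. Equal losses of one patient do not cancel, because the arms differ in size.

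**Range for early scanning.** Let p be the true moderate-or-severe rate, e the share of controls scanned early and m the share of their cases missed. The control rate is understated by p × e × m.

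- Lowest inputs: 1/6 × 1/6 × 0.25 = 0.7 points.
- Highest inputs: 1/2 × 1/2 × 1 = 25 points.

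The formula assumes that early-scanned controls carry the same risk as the others, which probably overstates the effect.

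**Range for one omitted severe patient.** With true rates from 1/6 to 1/2, the reported rate falls by 2.9 to 4.9 points in the drug arm (9/18 to 8/17; 3/18 to 2/17). In the control arm it falls by 10 to 16.7 points (3/6 to 2/5; 1/6 to 0/5).

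**Against sampling error.** Clopper-Pearson 95% intervals, the method named in SAP 4.5, are 4.3% to 77.7% for 2/6 and 13.3% to 59.0% for 6/18. Chance variation is larger than any of these shifts.

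**Effect of counting everyone.** If unscanned severe patients stay in the denominator and count as worst, the last three rows return to 6/18 against 2/6, a difference of 0. The first row is not corrected by counting. It can only be made visible by labelling the scan.

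**The case against.** A reader might infer several stronger statements that the documents do not support.

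- *The endpoint is biased, in a known direction.* Neither early discharge nor futility omission has a stated frequency, and the two can offset each other.
- *Scan time is fixed by arm.* Protocol 8.11.14 names no arm for the pre-discharge scan, and Protocol 5.2 foresees early discharge of drug patients. There is a tendency, not a rule.
- *The adopted guideline requires 72-96 h for this scan.* Protocol Appendix 7 says: "Optimal timing for initial CT assessment is at least 72-96 hours after onset of symptoms". That describes the best timing of an initial scan, counted from symptom onset. The Day 5 scan is a follow-up, and the item on follow-up CT gives no minimum.
- *The futility rule favours one arm.* It is the same in both and distorts the contrast only if its effect differs between arms.

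Other parts of the defence also stand. The discharge criteria suggested in Protocol 5.2 (pain resolved, normal diet tolerated, no sign of infection) mean that controls sent home early are probably the mildest, so the timing effect is likely to be near its low end. The SAP writes no explicit exclusion of unscanned patients; their loss follows from the no-imputation rule. Deaths and organ failure are listed, both severity classifications are tabulated, and scans are read centrally by a blinded reader.

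This limits the consequence but does not supply the missing rule. Blinded reading does not make scan times equal. Separate listings do not put an unscanned patient back into the CTSI denominator. The nearest-visit rule makes an early scan harder to recognise.

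**Conclusion.** The concern holds as a risk. Followed as written, SAP 4.8 and 7.2.1 allow an early scan to be reported as Day 5 and let the sickest patients leave the CTSI table, so the comparison between arms can be biased. Size and net direction are unknown. One control is about 17 points. The shifts of −3.9 to +16.7 points in the illustration rest on assumed rates of one third in each arm and on one patient per affected arm. The early-scan range of 0.7 to 25 points rests on assumed inputs throughout.

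Severity is minor to moderate. CTSI is a secondary, descriptive, untested endpoint in a 24-patient study whose primary endpoints are safety. With no test or model, however, the table is only as good as its labels and denominators.

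**What to change.** In SAP 7.2, before database lock:

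1. Use all randomized patients as the denominator of the CTSI category table. Add two rows: *not scanned: died before the scan or futility* and *not scanned: other reason*. Add a sensitivity table that ranks death before the scan or futility omission above severe.
2. Exempt the CECT from the nearest-visit rule in SAP 4.8. Label scans before Day 5 and after Day 7 as such. Report hours from pain onset (already recorded at Screening) and from randomization to scan, by arm, and list the early scans.

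Do not compare arms in a table restricted to scans at least 72 h after pain onset. That selects on discharge after randomization, would tend to remove the mildest controls, and could favour the drug.

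The cost is SAP wording and a few descriptive tables. Nothing changes in who is scanned or when. One small downside is that a death from a non-pancreatic cause counts as worst in the sensitivity table; a listing of causes can show this.

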7.2.2 Analysis

No statistical test will be performed on these variables.

7.2.3 Presentation

Each individual scale will be presented both by using summary statistics in tables and frequency tables.

The total scores will be presented using summary statistics.

7.3 Secondary Endpoints - PASS score

7.3.1 Definition

The definition of the PASS score is in accordance with the description below:

Calculated every 12 hours from 1st vital signs taken in the Emergency Department

Organ Failure Score: # Organs x 100 for each system

Organ Failure Definition: Modified Marshall Scoring System (adapted from Banks et al⁴)

Organ system	Score				
	0	1	2	3	4
Respiratory (PaO ₂ /FiO ₂)	>400	301–400	201–300	101–200	≤101
Renal					
Serum creatinine, µmol/L	≤134	134–169	170–310	311–439	>439
Serum creatinine, mg/dL	<1.4	1.4–1.8	1.9–3.6	3.6–4.9	>4.9
Cardiovascular (systolic blood pressure, mmHg) ^b	>90	<90, fluid responsive	<90, not fluid responsive	<90, pH <7.3	<90, pH <7.2

^aA score of 2 or more in any system defines the presence of organ failure

^bOff inotropic support

- Mechanical ventilation counts as respiratory organ failure
- New onset dialysis included as renal failure

SIRS (Systemic Inflammatory Response Syndrome): # SIRS Criteria satisfied x 25 for each criteria. (See below)

- Heart Rate > 90 beats per minute
- Temperature > 38 Celsius or < 36 Celsius
- White blood cell count < 4000 or > 12000
- Respiration > 20/minute

Take the most extreme value within each 12 hour window

Take the WBC from the most recent prior CBC if none available in a given 12 hour window

Abdominal Pain Score: Abdominal pain (0-10) x 5

- Highest numerical value in each 12 hour window

Morphine Equivalent Dose Score: Morphine Equivalent Dose x 5

- For consistency will be using IV MED (typical MED is for oral)
- Common conversions: (easiest to convert to IV)
- Morphine IV to PO is 1 to 3 (ie morphine 10 mg IV = 30 mg PO)
- Dilaudid IV to PO is 1 to 4 (ie dilaudid 1.5 mg IV = 7.5 mg PO)
- Dilaudid IV to Morphine IV is 1:7
- Note: 1 po MED = 30 mg oral morphine
- (refer to tables for more specific conversion)

	Parenteral	Oral
Morphine	10	30
Buprenorphine	0.3	0.4 (sl)
Codeine	100	200
Fentanyl	0.1	NA
Hydrocodone	NA	30
Hydromorphone	1.5	7.5
Meperidine	100	300
Oxycodone	10	20
Oxymorphone	1	10
Tramadol	100	120

Equianalgesic dose conversions. For calculation of Pancreatitis Activity Score:

1 MED (morphine equivalent dose) = 1 mg parenteral morphine = 3 mg oral morphine.

Tolerating Solid Diet Score: (yes=0, no=1) x 40

- Retrospective analysis: based on change in diet order
- Prospective analysis: tolerating at least 50% of solid meal without increase abdominal pain or vomiting

Then calculate the total score including absolute and percent change from baseline

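### SAP 7.3.1 scores PASS every 12 hours from emergency-department vital signs, but the protocol schedules pain, creatinine and oxygenation once daily from randomization; its hydromorphone rule also contradicts its own example

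*SAP*

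**What the plan says.** SAP 7.3.1 defines PASS as the sum of five terms: organ failures (100 points each), SIRS criteria (25 each), abdominal pain 0-10 (times 5), morphine-equivalent dose (times 5) and solid-diet intolerance (40). The timing is "Calculated every 12 hours from 1st vital signs taken in the Emergency Department". Pain is the "Highest numerical value in each 12 hour window". The organ count uses creatinine, PaO2/FiO2 and systolic pressure, with ventilation and new dialysis counting as failures. One missing-input rule is given: "Take the WBC from the most recent prior CBC if none available in a given 12 hour window".

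For opioids, 7.3.1 states "Dilaudid IV to PO is 1 to 4 (ie dilaudid 1.5 mg IV = 7.5 mg PO" and "Dilaudid IV to Morphine IV is 1:7", then says "refer to tables for more specific conversion". It also contains "Note: 1 po MED = 30 mg oral morphine", while the unit given with the equianalgesic table is "1 MED (morphine equivalent dose) = 1 mg parenteral morphine = 3 mg oral morphine".

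SAP 4.8 allows no imputation, apart from moving unscheduled values to the nearest visit with missing data. SAP 7 presents all parameters by visit, and 7.3.3 plots mean PASS by visit.

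Protocol 8.2 to 8.6 schedule vital signs and CBC at 12, 36, 60, 84 and 108 h from randomization, plus an adverse-event check at 12 h. The pain scale, chemistry and SpO2/FiO2 appear only in the daily blocks. Protocol 8.11.9 confirms two CBCs but one chemistry profile per day on Days 1-5. Protocol 8.11.6 records blood gases on Days 1, 5 and 10 only, and only if already done for care. Protocol 8.1 asks for the times of pain onset and of consent.

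**The concern.** The scoring rule asks for inputs that the protocol does not schedule, at times counted from an event that the protocol does not ask sites to record. The presentation sections are built on visits and do not say whether the 12-hour assessments count as visits. Two competent programmers could therefore produce different PASS series from the same records. One might score daily visits only. Another might score every 12 hours and total whatever is present, and those intermediate totals would fall for lack of data and not because the patient improved.

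The opioid term has a separate problem: the same hydromorphone dose can receive different points depending on which line of 7.3.1 is applied. In an open-label study, it is better to settle both matters before the data are summarised than after.

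**Working it through.** **Timing.** Inputs: assessment times from protocol 8.2 to 8.8, Appendix 11 (footnote e) and 8.11.9.

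- Twelve-hour times on Days 1-5, anchored at randomization: 0, 12, 24, ..., 108 h = 10.
- Times with pain, creatinine and SpO2/FiO2 scheduled: 0, 24, 48, 72, 96 h = 5.
- Times without them: 12, 36, 60, 84, 108 h = 10 - 5 = 5.
- For a patient still in hospital at 216 h: 19 times, 10 daily visits, 9 intermediate. At 132, 156, 180 and 204 h nothing is scheduled.

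This count assumes a randomization anchor. The documents do not give the gap between the emergency-department vital signs and randomization, so gaps of 0 to 24 h were tried. If the gap is a multiple of 12 h, 5 of 10 windows lack the three inputs. For the other gaps tried, it is 6 of 11, counting part windows.

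Protocol Appendix 8 asks for pain at that moment, so even at a daily visit one reading is not a 12-hour maximum. PaO2 is available on at most 3 of the 10 daily visits (0, 96, 216 h). A daily respiratory item therefore needs the SpO2/FiO2 route, which SAP 7.7.1 and protocol Appendix 2 use but SAP 7.3.1 does not mention.

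**Points involved if a term is left out.** Pain: 0 to 50; at an assumed 6/10, 6 x 5 = 30. Respiratory and renal items: 0 to 2 x 100 = 200. The upper end requires both failures to be detectable only from oxygenation and creatinine, because ventilation and renal replacement are recorded with vital signs (protocol 8.11.5), hence every 12 hours on Days 1-5.

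**Hydromorphone.** As a control, the morphine rule reproduces: 30/10 = 3, as stated. The hydromorphone rule does not: 7.5/1.5 = 5, from both the in-line example and the table row, against a stated 4. The table's parenteral ratio to morphine is 10/1.5 = 6.67, against a stated 7.

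PASS points for 7.5 mg oral hydromorphone, at 5 points per mg of parenteral morphine:

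| Route | Calculation | Points |
|---|---|---|
| Table | 7.5 x (10/7.5) x 5 | 50 |
| 1:5, then 1:7 | (7.5/5) x 7 x 5 | 52.5 |
| 1:4, then 6.67 | (7.5/4) x (10/1.5) x 5 | 62.5 |
| 1:4, then 1:7 | (7.5/4) x 7 x 5 | 65.6 |

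The 1:4 rule alone adds 12.5 points (25%). Adding 1:7 brings the excess to 15.6 points (31%).

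**The case against.** The strongest reply is that 7.3.1 transcribes a general description of the instrument (it even keeps a rule for retrospective analysis), while SAP 7 and 7.3.3 show that PASS will be reported by visit. On that reading, nobody has to compute a score without inputs. This stands in part: a reader might infer that the SAP forces missing or partial intermediate scores, and it does not. But the by-visit sections do not withdraw the 12-hour grid or say whether the 12-hour assessments are visits.

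A reader might also infer that intermediate organ items would be set to zero, because SAP 7.7.1 treats absent data as no organ failure. That rule belongs to a different endpoint, and 7.3.1 has its own organ-failure definition; nothing in the SAP imports the rule.

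The lack of PaO2 does not mean that daily scores lack oxygenation data. SpO2/FiO2 is collected daily and already serves SOFA and respiratory failure, so a cross-reference is enough. SAP 4.8 may also fill some gaps from unscheduled values, but only where such values exist.

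On opioids, the table is accompanied by text saying that it is for calculating the Pancreatitis Activity Score, so it probably governs, although the SAP stops short of saying so. The gap between 1:7 and 6.67 is rounding. The 31% figure needs oral hydromorphone and both text rules chained, and the documents do not say how much oral hydromorphone will be used. The oral-MED note might be read as a tenfold error (30 mg oral morphine as 1 MED, 5 points, or 10 MED, 50 points). But 7.3.1 states that the score uses IV equivalents and fixes the unit, so the note is a conflicting remark to be cleared up and does not establish a tenfold scoring error.

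**Conclusion.** The point holds as a specification conflict. The 12-hour scoring rule does not match the scheduled data: 5 of 10 times on Days 1-5 lack pain, creatinine and SpO2/FiO2 if the grid is anchored at randomization, and about half the windows do under an emergency-department anchor with an assumed gap. The reporting sections conflict with the grid without resolving it. The hydromorphone rule contradicts its own example and the table, worth 12.5 points on a 50-point term for 7.5 mg orally, or 15.6 with both text rules.

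The 30-point pain figure rests on an assumed score of 6/10, and the 200-point organ figure is a ceiling, not an expected effect. The documents do not support reading this as a bias between arms or a threat to the study's conclusions: both arms share the schedule, PASS is one of many descriptive secondary endpoints, SAP 7.3.2 plans no analysis of it, and the primary endpoints are safety measures.

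**What to change.** Before database lock:

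1. In SAP 7.3.1, replace the emergency-department 12-hour grid with the randomization-timed daily visits as the scored times, in line with SAP 7 and 7.3.3. Use that visit's pain score and creatinine, and SpO2/FiO2 where no PaO2 exists. Protocol Appendix 1 lists SpO2/FiO2 of 315 or less alongside PaO2/FiO2 of 300 or less, and 300 is the upper limit of the Marshall score of 2 that defines organ failure for PASS. State one fixed look-back window for SIRS and opioids where the data allow. Vital-sign extremes are recorded since the prior assessment, which means 12 h at the 24 to 120 h visits but 24 h at 144 to 216 h. Combining the two records per day through 120 h would give a uniform 24 h. Also state the source of the opioid term at 0 h, because protocol 8.11.2 specifies timed doses only from Day 1.

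   Alternatively, if 12-hourly scores are kept on Days 1-5, anchor them to randomization, state a carry-forward rule for pain, creatinine and oxygenation like the one for white cells, and do not total scores with missing components.

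2. Reconcile the hydromorphone lines and the oral-MED note with the equianalgesic table and the MED definition, so that one source is used for scoring. This review takes no view on which conversion is clinically right.

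The cost is SAP wording and programming on data already to be collected. Daily scoring gives coarser timing and a spot pain reading in place of a 12-hour maximum. A 24-hour look-back departs from the 12-hour windows in 7.3.1 and, at a constant rate of opioid use, doubles that term. Carry-forward makes the pain, creatinine and oxygenation components lag by 12 h.

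### SAP 7.3.1 gives conflicting opioid conversions for the PASS score: an oral unit ten-fold away from the designated one, and hydromorphone ratios that disagree with the section's own table

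*SAP*

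**What the plan says.** SAP 3.1.4 lists PASS among the secondary efficacy endpoints. SAP 7.3.1 adds up five items: organ failure (100 per system), SIRS (25 per criterion), abdominal pain (0 to 10, times 5), opioid use, and failure to tolerate a solid diet (40). The opioid item reads "Morphine Equivalent Dose Score: Morphine Equivalent Dose x 5".

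The section then says how to obtain the MED:

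- Choice of unit: "For consistency will be using IV MED (typical MED is for oral").
- Morphine by route: "Morphine IV to PO is 1 to 3 (ie morphine 10 mg IV = 30 mg PO").
- Hydromorphone by route: "Dilaudid IV to PO is 1 to 4 (ie dilaudid 1.5 mg IV = 7.5 mg PO").
- Hydromorphone to morphine: "Dilaudid IV to Morphine IV is 1:7".
- An oral unit: "Note: 1 po MED = 30 mg oral morphine".
- A pointer to tables for more specific conversions, followed by a table of parenteral and oral doses by drug (morphine 10 and 30 mg, hydromorphone 1.5 and 7.5 mg, and others).
- A closing definition introduced by "Equianalgesic dose conversions. For calculation of Pancreatitis Activity Score", which reads "1 MED (morphine equivalent dose) = 1 mg parenteral morphine = 3 mg oral morphine".

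The total is to be reported with absolute and percent change from baseline (SAP 7.3.1). SAP 7.3.2 plans no analysis of it. SAP 7.3.3 plans summary tables and graphs of the mean at each visit with 2 standard errors. The protocol does not define PASS, and Protocol 10.4 leaves all statistical analyses to the SAP.

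**The concern.** One scored item has two definitions of its unit, and they give oral doses values ten-fold apart. The note sits in the same list as the conversions meant for use, and nothing says that it is not used for PASS. It is also the only line in that list that defines a unit specifically for oral doses. A programmer could take it as the rule for oral opioids, or could take each oral entry in the table as one MED.

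The hydromorphone lines raise a separate problem. They are offered as conversions to apply, yet the stated IV-to-oral ratio does not match the example in its own parentheses, and neither ratio matches the table. Two programmers working from this section could therefore score the same hydromorphone record differently without either ignoring an instruction.

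The conversion will be run on real route data, because Protocol 8.11.2 collects the route and the time of each pain-medication dose. What is at stake is whether the reported PASS values mean what they are said to mean.

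**Working it through.** **Inputs**, all from SAP 7.3.1: item score = MED × 5; designated unit, 1 MED = 1 mg IV morphine = 3 mg oral morphine; the note's unit, 30 mg oral morphine; table rows for morphine (10 parenteral, 30 oral) and hydromorphone (1.5 parenteral, 7.5 oral); stated hydromorphone ratios 1:4 and 1:7. The doses below are the table's own entries, used as examples, not a forecast of use.

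**1. The plan's own equivalence, in the designated unit.**

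- 10 mg IV morphine: 10 / 1 = 10 MED; 10 × 5 = 50 points.
- 30 mg oral morphine: 30 / 3 = 10 MED; 10 × 5 = 50 points.

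The designated unit, the morphine ratio and the table agree.

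**2. The note's unit.** 30 mg oral morphine: 30 / 30 = 1 MED; 1 × 5 = 5 points. The gap is 50 − 5 = 45 points, a factor of 30 / 3 = 10. The factor is the same for every oral opioid in the table that is converted through 30 mg of oral morphine: 20 mg of oral oxycodone, for instance, scores 50 or 5.

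**3. Equivalent doses by IV and oral route, under each use of the units.**

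| Unit for IV | Unit for oral | 10 mg IV | 30 mg oral | Change |
|---|---|---|---|---|
| Designated | Designated | 50 | 50 | 0 |
| Note | Note | 10 × 3 / 30 × 5 = 5 | 5 | 0 |
| Designated | Note | 50 | 5 | −45 (−90%) |

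A change between routes appears only in the last row, where the units are mixed. In the second row there is no such change, but the whole opioid item is one tenth of its designated size relative to the other items.

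**4. Hydromorphone.**

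- IV to oral: stated 1:4; the example and the table give 7.5 / 1.5 = 5.
- IV hydromorphone to IV morphine: stated 1:7; the table gives 10 / 1.5 = 6.67.
- 7.5 mg oral by the stated ratios: 7.5 / 4 = 1.875 mg IV hydromorphone; 1.875 × 7 = 13.125 MED; 13.125 × 5 = 65.6 points.
- 7.5 mg oral by the table: 10 MED; 50 points. Excess 65.6 / 50 − 1 = 31%.
- 1.5 mg IV by the stated ratio: 1.5 × 7 × 5 = 52.5 points, against 50 by the table (5% more).

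Most of the excess for oral doses comes from the 1:4. Using 1:5 with 1:7 gives 7.5 / 5 × 7 × 5 = 52.5 points.

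**5. Scale.** The 45-point gap exceeds the whole diet item (40) and is close to two SIRS criteria (2 × 25 = 50). Under the planned 3:1 allocation in cohorts of 4, 4, 8 and 8, supportive care has 1 + 1 + 2 + 2 = 6 patients. If all six contribute to a mean and one has 30 mg of oral morphine scored by the note, that mean moves by 45 / 6 = 7.5 points. One patient with 7.5 mg of oral hydromorphone scored by the stated ratios moves it by 15.6 / 6 = 2.6 points.

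**The case against.** The strongest reply is that the section already settles the unit. It says that the IV MED will be used, sets the usual oral MED aside, and ties the 1 mg and 3 mg definition to the calculation of this score. The note names a different unit and no scoring instruction calls on it. Read that way, 10 mg IV and 30 mg oral morphine both score 50. This stands, and it limits the first conflict to a risk of misreading.

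A reader might go further and infer that PASS falls by 90% whenever a patient moves from IV to oral opioids, so that an arm that switches earlier looks better. The documents do not support this. The fall needs the designated unit for IV doses and the note's unit for oral doses, against two explicit lines. Nothing in the protocol or SAP says how often or when patients change route, or that this would differ by arm.

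It can also be said that PASS is one of many descriptive secondary endpoints and that no test or decision rule rests on it. That is correct, but a descriptive mean is not protected from a unit error, and these means are to be tabulated and graphed.

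The reply does not reach the hydromorphone lines. The pointer to the tables for more specific conversions suggests that the table should prevail, but the section does not say so, and the ratios stand as common conversions.

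**Conclusion.** The concern holds in two parts of different strength.

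- **The oral-unit note** is a real ten-fold conflict in the text, but only a risk of mis-scoring. The designated unit is identifiable and treats the routes alike. The size if the note is applied is 5 points in place of 50 for 30 mg of oral morphine.
- **The hydromorphone ratios** are a plain contradiction between conversions all offered for use: 1:4 against 1:5, and 1:7 against 6.67. Together they give 65.6 points against 50 for 7.5 mg of oral hydromorphone (+31%).

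These figures rest only on the section's own entries. How far the reported PASS means would move depends on how much oral opioid and hydromorphone is used and on how the section is programmed, neither of which the documents give. The effect is confined to PASS means, absolute and percent changes, and graphs. No planned inference changes.

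**What to change.** For scoring only, in SAP 7.3.1:

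1. Delete the oral-unit note, or mark it *not used for PASS*.
2. Reconcile the two hydromorphone ratio lines with the table, or remove them.
3. State that every opioid, by any route, is converted to mg of IV morphine from the equianalgesic table, and that one MED is 1 mg IV or 3 mg oral morphine. As a formula: MED = dose × 10 / table entry for that drug and route. This gives 10 MED for 30 mg oral morphine, for 1.5 mg IV hydromorphone and for 7.5 mg oral hydromorphone.

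Naming the table makes the score internally consistent. It is not a statement about how analgesics should be given. A drug or route with no table entry would need its own stated rule.

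The cost is a few lines of SAP text before database lock. No new data are needed, and any score already computed in the designated unit from the table is unchanged.
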